## LIST OF ABBREVIATIONS AND DEFINITION OF TERMS

Abbreviation	Definition
ADA	anti-drug antibody
AE	adverse event
AERO	adverse event reporting online
AESI	adverse event of special interest
AUC	area under the curve
CIOMS	Council for International Organizations of Medical Sciences
ClinRO	clinician-reported outcome
C max	maximum concentration observed
CTCAE	Common Terminology Criteria for Adverse Events
DSUR	Development Safety Update Report
EC	Ethics Committee
eCRF	electronic Case Report Form
EDC	electronic data capture
EMA	European Medicines Agency
FDA	U.S. Food and Drug Administration
HA	hemagglutinin complex
HAHA	human anti-human antibody
HBV	hepatitis B virus
HBcAb	hepatitis B core antibody
HBsAg	hepatitis B surface antigen
HCV	hepatitis C virus
HIPAA	Health Insurance Portability and Accountability Act
IB	Investigator's Brochure
ICH	International Council for Harmonisation
ICU	intensive care unit
iDMC	independent Data Monitoring Committee
IMP	investigational medicinal product
IND	Investigational New Drug (Application)
IRB	Institutional Review Board
IRC	Independent Review Committee
IRF	Independent Review Facility
IxRS	interactive voice or web-based response system
LPLV	last patient, last visit
M2	matrix-2
mITT	modified intent-to-treat (influenza) infected (population)
MN	mobile nursing
NA	neuraminidase

Abbreviation	Definition
NAI	neuraminidase inhibitor
NCI CTCAE	National Cancer Institute Common Terminology Criteria for Adverse Events
NGS	next-generation sequencing
ObsRO	observer-reported outcome
OS	overall survival
PFS	progression-free survival
PK	pharmacokinetic
PRO	patient-reported outcome
PRO-CTCAE	Patient-Reported Outcomes version of the Common Terminology Criteria for Adverse Events
RIDT	Rapid Influenza Diagnostic Test
RT-PCR	reverse transcriptase-polymerase chain reaction
SAE	serious adverse event
SAP	Statistical Analysis Plan
SOC	standard of care
SUSAR	suspected unexpected serious adverse reaction
TCID 50	50% tissue culture infectious dose
t max	time to maximum concentration
TQT	Thorough QT
TTAS	time to alleviation of symptoms
TTCI	time to clinical improvement
TTIIS	time to improvement of influenza symptoms
ULN	upper limit of normal
USPI	U.S. Package Insert
Vc/F	apparent volume of distribution for the central compartment
WES	whole exome sequencing
WGS	whole genome sequencing

## 1. **BACKGROUND**

### 1.1 **BACKGROUND ON INFLUENZA**

Influenza is an acute respiratory infectious disease caused by a virus of the orthomyxovirus family. Two forms are known to infect humans, influenza A and B. These viruses cause an acute febrile infection of the respiratory tract after an incubation period of 1 to 4 days, characterized by the sudden onset of fever, cough, fatigue, headache, and myalgia. Annual influenza epidemics are thought to result in between 3 and 5 million cases of severe illness, and between 250,000 and 500,000 deaths every year around the world (WHO 2017).

Although the condition is usually self-limiting in healthy adults, it can be associated with substantial morbidity and occasional mortality in children, the elderly, and the immunocompromised (Paules and Subbarao 2017).

Hospitalization due to severe influenza is associated with high mortality (4%–8%), intensive care unit (ICU) admission (5%–17%), and prolonged hospital stays of between 5 and 9 days. During a pandemic season, the outcomes may be more serious, with up to 34% of patients requiring ICU care and a mortality rate as high as 15% (Lee and Ison 2012).

The influenza viruses have a segmented, negative-sense, single-stranded, lipid-encapsulated RNA genome; they range between 80 and 100 nm in size. Subtypes are defined according to glycoproteins present in the viral lipid coat. The hemagglutinin complex (HA) is the major surface protein of the virus. The neuraminidase (NA) proteins are the second major surface proteins in the virion and play a role in enhancing virus penetration of the mucus layer around the target cell and in release of virus from the cell surface. The matrix-2 (M2) protein triggers the disintegration of the virion during virus entry into the cell and may also be involved in protecting the HA prior to assembly of new virus particles.

In addition to Xofluza, the following anti-influenza virus drugs are currently available for treatment of acute, uncomplicated influenza in different countries: the M2 ion channel inhibitors amantadine and rimantadine, the RNA polymerase inhibitor favipiravir, and the NA inhibitors (i.e., oseltamivir, zanamivir, and peramivir). Many cases of seasonal influenza infection are resistant to amantadine and rimantadine, hence their use in clinical practice is limited. NA inhibitor (NAI) oral formulations need to be administered for 5 days, potentially resulting in poor patient compliance and convenience, while inhalation formulations can only be used in patients who are able to inhale the drug. These factors contribute to an unmet medical need for new antiviral influenza drugs that can be easily and less frequently administered, particularly in patients who are severely ill and possibly intubated.

In February 2019, intravenous zanamivir (Dectova®) received a positive opinion for use under exceptional circumstances from the European Medicines Agency for the treatment of complicated and potentially life-threatening influenza A or B virus infections in adult and pediatric patients (aged  $\geq 6$  months). Zanamivir is only indicated when the influenza virus is resistant to other antiviral drugs, or when other antiviral drugs are not suitable, and, therefore, have limited scope in treating influenza in hospitalized patients. Currently, there are no other licensed drugs specifically approved for the treatment of influenza in hospitalized patients. Despite this, NAs are widely used as the mainstay of treatment for hospitalized patients, and evidence shows a potential reduction in mortality in hospitalized patients treated with NAs, especially if initiated as early as possible (Muthuri et al. 2014).

Influenza viruses are known to mutate during the course of replication and can mutate into a strain resistant to existing antiviral influenza drugs or a strain to which most people are not immune. Certain strains of avian influenza have been found to be highly pathogenic with high rates of NA-resistance (Hu et al. 2013). New antiviral influenza treatments with novel mechanisms of action may provide alternative therapy options, particularly when used in combination with NAs, to overcome such highly pathogenic organisms.

## **1.2 BACKGROUND ON XOFLUZA**

Xofluza (also referred to as baloxavir marboxil) is a compound that exerts antiviral effects against influenza. Xofluza is a pro-drug, which is converted to an active form baloxavir through a metabolic process called hydrolysis, in the blood, liver, and small intestine.

Xofluza acts on cap-dependent endonuclease, an enzyme specific to influenza viruses, and inhibits viral cap-snatching, thereby suppressing the replication of influenza viruses.

To date, one Phase II study in otherwise healthy adults and two Phase III studies in adults and adolescents (i.e., one in otherwise healthy patients and one in patients with high risk of influenza-related complications) have been completed and are summarized below. Xofluza is now indicated for treatment of acute uncomplicated influenza in patients who have been symptomatic for no more than 48 hours and who are otherwise healthy adults and pediatric patients 5 years of age and older. Also, Xofluza has been approved for post-exposure prophylaxis of influenza in patients 5 years of age and older following contact with an individual who has influenza.

Xofluza is approved for use in Japan (since February 2018) for the treatment of influenza A or B virus infection in all age groups ( $\geq 10$  kg) and in the United States (since October 2018), Hong Kong (since February 2019), and Thailand (since

March 2019). In the US It is approved for the treatment of influenza in otherwise healthy patients aged 12 years and above who have been symptomatic for no more than 48 hours as well as pediatric patients 5 years of age and older. In addition, Xofluza is approved in Thailand for the treatment of influenza in patients aged 12 years and above who have been symptomatic for no more than 48 hours and are at high risk of developing influenza-related complications as well as post-exposure prophylaxis. Regulatory filings in other global regions are either completed, ongoing, or planned to gain market authorization for the use of Xofluza for the treatment of influenza.

Detailed profiles of Xofluza are provided in the Xofluza Investigator's Brochure.

### **1.2.1 Overview of Xofluza Clinical Development**

The efficacy and safety of Xofluza have been established in randomized placebo-controlled Phase 2 and 3 studies. In clinical studies in adult and adolescent patients who were otherwise healthy (Phase 3 study T0831 and Phase 2 study T0821) or at high risk of developing influenza complications (Phase 3 study T0832), Xofluza was shown to be efficacious and well tolerated. Clinical efficacy was demonstrated against both influenza A virus subtypes (A/H1N1 and A/H3N2) and against type B virus. The potent antiviral effect of Xofluza was also seen in terms of the median time to cessation of viral shedding by virus titer, with at least a 2-day reduction over placebo and, in the Phase 3 studies in which oseltamivir was included as an active control group (T0832 and T0831), a 2-day reduction over oseltamivir. Xofluza is unique in achieving this degree of anti-viral effect with a single oral dose administration.

#### **1.2.1.1 Efficacy**

In the Phase 3 double-blind randomized study in otherwise healthy patients (Study 1601T0831/CAPSTONE-1; Hayden et al. 2018), efficacy and safety of a single dose of Xofluza in adult and adolescent patients with influenza were investigated. Doses studied were 40 mg for patients who weigh < 80 kg and 80 mg for patients who weigh  $\geq$  80 kg. The median time to alleviation of symptoms was 53.7 hours in the Xofluza group compared with 80.2 hours in the placebo group. The difference in the median time was  $-26.5$  hours between the Xofluza group and the placebo group. The Xofluza group showed a significantly greater reduction in the time to alleviation of symptoms compared with the placebo group (two-sided P value  $< 0.0001$ ). In the adult stratum of patients, the median time to alleviation of symptoms was 53.5 hours in the Xofluza group compared with 53.8 hours in the oseltamivir group, and no significant difference was found.

A phase 3 open-label study in otherwise healthy pediatric patients (Study 1618T0822) investigated the efficacy of a single dose of Xofluza in patients aged 6 months to 11 years. Dosages studied were 5, 10, 20 and 40 mg for patients weighing 5 to < 10 kg, 10 to < 20 kg, 20 to < 40 kg and  $\geq$  40 kg, respectively. The

median time to alleviation of influenza illness, i.e., alleviation of cough, nasal discharge/nasal congestion and fever, (primary endpoint) was 44.6 hours. The median time to resolution of fever (a secondary endpoint) was 21.4 hours.

A phase 3 double-blind randomized study in people aged 12 years or older who were at a high risk of complications from the flu (N=2184; Study 1601T0832/CAPSTONE-2) compared the efficacy of a single oral dose of Xofluza (40 mg or 80 mg according to body weight) with placebo or 75 mg of oseltamivir twice a day for 5 days. The time to improvement of influenza symptoms (TTIIS) was significantly shorter with Xofluza than placebo (median 73.2 vs 102.3 hours,  $p<0.0001$ ) and numerically shorter than oseltamivir (81.0 hours,  $p=0.8347$ ). TTIIS in patients with A/H3N2 virus was shorter with Xofluza than with placebo (median: 75.4 vs 100.4 hours;  $p=0.0141$ ). TTIIS in patients with influenza B was also significantly shorter with Xofluza (74.6 hours) than either placebo (100.6 hours;  $p=0.0138$ ) or oseltamivir (101.6 hours;  $p=0.0251$ ).

The safety and effectiveness of Xofluza in otherwise healthy pediatric subjects 5 to less than 12 years of age is supported by one randomized, double-blind, controlled trial, Trial CP40563 with a primary endpoint of safety. In this trial, 118 otherwise healthy pediatric subjects were randomized and treated in a 2:1 ratio and received either Xofluza (N=79) or oseltamivir (N=39). Efficacy was extrapolated from adults and adolescents based on comparable pharmacokinetic (PK) exposures in adults, adolescents and pediatric subjects 5 to less than 12 years of age. The median time to alleviation of signs and symptoms in influenza-infected subjects was comparable in the Xofluza and oseltamivir arms. Adverse events (AEs) reported with Xofluza in pediatric subjects were similar to those observed in adults and adolescents except for vomiting and diarrhea, which were both more commonly reported in pediatric subjects.

The safety and effectiveness of Xofluza for post-exposure prophylaxis in pediatric and adolescent subjects 5 to less than 18 years of age is supported by one randomized, double-blind, controlled trial conducted in Japan Trial T0834. Subjects in this trial were randomized in a 1:1 ratio to receive Xofluza or placebo. A total of 69 subjects from 5 to < 18 years of age in Trial T0834 received Xofluza. The incidence of reverse transcriptase-polymerase chain reaction (RT-PCR)-confirmed symptomatic influenza in pediatric subjects 5 to < 18 years of age was similar to that observed in adult subjects. Efficacy was extrapolated from adults based on comparable PK exposures in adults, adolescents and pediatric subjects 5 to < 18 years of age. Adverse events reported in pediatric and adolescent subjects were similar to those reported in adults in the same trial.

### **1.2.1.2 Safety**

In the phase 3 double-blind randomized study in otherwise healthy patients (Study 1601T0831/CAPSTONE-1), patients in the 20 to 64 years of age stratum

received a single dose of 40 or 80 mg (depending on the patient's weight) of Xofluza, repeated dose of 75 mg oseltamivir twice daily for 5 days, or placebo, and patients in the 12 to 19 years of age stratum received a single dose of 40 or 80 mg (depending on the patient's weight) of Xofluza or placebo. A total of 1,432 patients received the study drug: 610 in the Xofluza group, 309 in the placebo group, and 513 in the oseltamivir group. No deaths were reported in all the 3 groups. Two serious adverse events (SAEs) (1 event each of meningitis viral and incarcerated inguinal hernia) were reported in 2 of 610 patients (0.3%) in the Xofluza group. The events resolved and were considered not related to the study drug. A total of 9 AEs leading to withdrawal of study drug were reported: 3 events in 2 of 610 patients (0.3%) in the Xofluza group, 4 events in 1 of 309 patients (0.3%) in the placebo group, and 2 events in 2 of 513 patients (0.4%) in the oseltamivir group. All of the AEs leading to withdrawal of study drug in the Xofluza group were considered not related to the study drug.

In the phase 3 double-blind randomized study in people 12 years or older who were at a high risk of complications from the flu (N=2184; Study 1602T0832/CAPSTONE-2), the incidence of any adverse event (25.1–29.7%) or any serious adverse events (0.7–1.2%) did not differ significantly between the groups treated with a single oral dose of Xofluza (40 mg or 80 mg according to body weight), placebo, or 75 mg of oseltamivir twice a day for 5 days.

In the phase 3 open-label study in otherwise healthy pediatric patients (Study 1618T0822), 2, 31, 66, and 8 patients (a total of 107) received a single 5, 10, 20, and 40 mg dose of Xofluza, respectively. No deaths, serious AEs or discontinuations due to AEs were reported in the study.

In the phase 3 open-label study in otherwise healthy pediatric patients (weighing  $\leq$  20 kg and aged  $\leq$  12 years) with influenza (Study 1705T0833), a total of 33 patients received a single dose of Xofluza. The dosage was 10 mg of Xofluza in patients weighing  $\geq$  10 kg and 1 mg/kg of Xofluza in patients weighing  $<$  10 kg. No deaths, serious AEs or discontinuations due to AEs were reported in the study. Most common AEs reported were vomiting, diarrhea and pharyngitis. Treatment-related AEs (assessed by the investigator) were reported in 1 of 33 patients (3.0%, 1 event of platelet count increased). All AEs were classified as Grade 1 or 2. All AEs resolved or were resolving.

In a placebo-controlled clinical trial (post-exposure prophylaxis of influenza), Trial T0834, conducted in adults, and pediatric subjects  $\geq$  5 years of age, a total of 360 subjects received Xofluza, of which 291 (81%) were adults  $\geq$  18 years; 12 (3%) subjects were adolescents  $\geq$  12 to 17 years and 57 (16%) were pediatric subjects 5 to  $<$  12 years of age. The safety profile was similar in pediatric patients ages 5 to  $<$  12 years old as that reported in adults and adolescents 12 years of age and older.

Refer to the Xofluza Investigator's Brochure for details on nonclinical and clinical studies.

### **1.2.2 Post-Marketing Safety Data**

Hypersensitivity reactions have been observed in the post-marketing setting which include reports of anaphylaxis/anaphylactic reactions and less severe forms of hypersensitivity reactions including angioedema, and urticaria.

Refer to Section 6 of the Xofluza Investigator's Brochure for current details relating to post-marketing safety information.

## **1.3 STUDY RATIONALE AND BENEFIT-RISK ASSESSMENT**

Seasonal influenza is a major burden to global health. There are an estimated 3-5 million cases of severe disease worldwide and approximately 290–650 thousand people die from influenza annually (WHO 2017a, WHO 2018, Baxter 2016). Influenza also places significant demands on healthcare services each season, and impacts society through lost workforce productivity (WHO 2018). Annual vaccination programs are the cornerstone of attempts to prevent influenza infections, but the effectiveness of these programs is variable due to both suboptimal uptake of vaccinations and mismatches between the vaccine and circulating influenza strains (CDC 2017). Consequently, the need for antiviral agents remains high.

Influenza A and B viruses are highly contagious (Vanderlinden and Naesens 2014). Most individuals with influenza infection are advised to stay at home until they have been afebrile for at least 24 hours, which puts other household members at risk of infection (CDC 2018a). Once one household member is infected with influenza, the risk of transmission to a household contact can be up to 38%, with a delay between onset in the index patient and infection of the household contact of around 3 days (Tsang et al. 2016).

Successful methods to mitigate the spread of respiratory viruses, including COVID-19 and influenza, through testing include identifying and deploying testing capacity to communities where viral transmission is highest and communities where insufficient testing is being conducted. We have developed a data-analytics driven algorithm based on laboratory data and the social vulnerability index (SVI) that identifies testing deserts and hot spots to identify vulnerable communities with active spread of respiratory infection (hot spots) and locations without enough testing penetration to effectively determine viral activity (testing deserts).

It has been well described that socially vulnerable communities lack access to testing because testing locations may not be able to be reached by public transportation, long wait times because of centralized testing locations and lack of testing hours outside of the traditional work-day (5-10). Mobilization of a

COVID-19 and influenza testing unit to communities where individuals already gather for other social events provides increased access to testing addresses many of these challenges that are experienced in underserved and socially vulnerable communities. However, identification and testing of individuals who may reside in hot spots for respiratory viruses is not sufficient to completely mitigate the spread of disease or reduce the effects of infection. Rapid access to effective therapeutics within the narrow antiviral therapeutic window (48 hours from symptom onset) is necessary to reduce the spread of infection and reduce disease severity.

In this study will use our Respiratory Infection Hot Spot Algorithm that identifies and supports deployment of mobile testing units to community centers, parks and senior centers in socially and economically disadvantaged communities to deploy a mobile test-to-treat model for Influenza A&B, along with testing for SARS-CoV-2 in socially vulnerable communities. Use of a point care test (POCT) for Influenza A&B and SARS-CoV-2 and a mobile pharmacist model enables the test-to-treat model that will target vulnerable communities that may lack access to testing and/or providers for treatment for influenza.

Xofluza is a first-in-class influenza antiviral that blocks RNA replication by inhibiting cap-dependent endonuclease activity (Omoto et al. 2018). Xofluza is administered by a convenient and unique one-dose, one-time regimen. In the Phase III CAPSTONE-1 double-blind randomized study in otherwise healthy patients (Hayden et al. 2018), a single treatment of Xofluza (40 mg for patients < 80 kg and 80 mg for patients  $\geq$  80 kg) significantly reduced the time to alleviation of symptoms compared with placebo and also effectively reduce viral load, as shown by a significant reduction compared with placebo in:

- The proportion of patients with positive influenza titer between Days 2 and 5
- The proportion with positive influenza virus RNA determined by PCR on Day 5
- The median time to cessation of viral shedding

Study ML44485 was therefore designed to use our Respiratory Infection Hot Spot Algorithm that identifies and supports deployment of mobile testing units to community centers, parks and senior centers in socially and economically disadvantaged communities to deploy a mobile test-to-treat model for Influenza A&B, along with testing for SARS-CoV-2 in socially vulnerable communities. This study will target communities with high rates of respiratory infection or insufficient testing for a screen and treat program for influenza. Matched communities based on the census track-based SVI will be compared to assess impact of the screen and treat program on influenza rates at a population level.

This study seeks to demonstrate that the laboratory can mitigate respiratory virus transmission in underserved populations through (1) use of analytics to identify

communities that are at risk for uncontrolled viral spread and (2) patient perception of a mobile screen and treat model for influenza.

In summary, there is a strong rationale and a positive benefit risk assessment for studying Xofluza in a screen and treat model for socially vulnerable communities and results from the Hayden et al study suggests that Xofluza has an acceptable clinical safety profile and could benefit patients who test positive for influenza. The benefit-risk ratio for Xofluza is expected to be acceptable in this setting.

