## **2. OBJECTIVES AND ENDPOINTS**

### **2.1 PRIMARY OBJECTIVE(S)**

This study seeks to demonstrate that the laboratory can mitigate respiratory virus transmission in underserved populations by using laboratory data to identify communities at risk for increase vial activity (hot spots) and intervening with a test-to-treat model provides increased access to influenza diagnostics and treatment in vulnerable and underserved communities.

1. The hot-spot frequency and hot spot score trend will be measured for each census tract to determine if the screen and treat intervention has an impact on reducing hot spot identification or hot spot score.
  - a. Following each mobile intervention, we will evaluate the hot spot score for the census tracts receiving a mobile screen and treat intervention and SVI-matched census tract not receiving an intervention for 14-days following the screen and treat intervention.
  - b. Patients will receive a follow-up phone call 14-days following their initial screening visit to assess patient and household symptoms and the socioeconomic impact of their test result and treatment access.

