## **3. STUDY DESIGN**

### **3.1 DESCRIPTION OF THE STUDY**

We have developed an analytic algorithm that uses measures from the CDC COVID-19 Hot Spot Criteria and Brown University School of Public Health to determine COVID-19 and Influenza Hot Spots and Testing Deserts, respectively.

The Hot Spot designation was based on the CDC county-specific Hot Spot criteria that has been used to deploy resources for interventions (i.e., laboratory testing, community mitigation, health communications and health care) specific needs for the communities of interest. The CDC hot spot criteria is based on COVID-19 rates at the county level. We have adapted these criteria in several ways: (1) we have narrowed the scope of the population of interest to the census tract (2) we have included influenza transmission data (3) we have based our calculations on the proportion of the respiratory virus testing performed by TriCore Laboratories relative to the total testing in the State of New Mexico (approximately 40%) and (4) we have incorporated social determinants of health data to aid in identifying the most vulnerable community. The adaptations to the criteria allows interventions to focus on a concentrated community and deliver the interventions in places that the community is already engaging, such as community centers, senior centers and parks. The identification of communities with insufficient testing to assess the respiratory virus transmission rate, or testing deserts, in our algorithm is based on the Brown University School of Public Health testing targets which has identified a goal of 532/100,000 or 1582/100,000 COVID-19 or influenza tests for as the minimum target or suppression target, respectively. The algorithm also incorporates the social vulnerability index in the testing desert tool.

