Using a longitudinal patient database with an active system to prospectively geocode addresses entered into our system, we are able to determine, at the census tract level, neighborhoods that are at high risk for viral transmission because they are a hot spot or testing desert. We are then able to incorporate the social vulnerability index as an additional weighted measure to the hot spot or desert score in order to calculate an identified hot spot or desert risk for a census tract. Through collaboration with local community centers, we are able to deploy a mobile testing unit to a community center, park or senior center that is in close proximity to the identified neighborhood for rapid onsite testing for Influenza A&B and SARS-CoV2 using the cobas Liat system.

New Mexico has adopted “New Mexico Board of Pharmacy Protocol for Pharmacists Prescribing of Dangerous Drugs in Conjunction with Point of Care Testing” (NMBOP POCT Protocol, Appendix 5) that allows pharmacists the prescriptive authority to prescribe Influenza antiviral therapy in conjunction with a positive point of care test (POCT). TriCore employs two (2) on-site clinical pharmacists who will follow all of the pharmacist mandates included in the regulation to prescribe and distribute Xofluza according to the approved protocol in the test-to-treat model presented in this study. The NMBOP PCOT Protocol documents the eligibility and requirements of the certified prescribing pharmacists (pharmacist) following this protocol.

The pharmacist will perform a screening physical assessment, health assessment and medical history for the patient. If the subject meets the inclusion criteria, they will have a point of care test performed. If the subject meets the exclusion criteria, they will be excluded from the study. Testing will be performed using the cobas® SARS-CoV-2 & Influenza A/B assay on the cobas® Liat® system from a self-collected nasal swab. Subjects who test positive for influenza A or B will be prescribed Xofluza with no additional refills. The pharmacist will follow-up with the patient 24-48 hours following administration for evaluation of

signs/symptoms and will refer the patient to their primary care provider, provider, or clinic for recommended laboratory testing and follow-up if appropriate.

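### Hot-spot deployments go to tracts chosen on the score they are then judged by, with controls matched on SVI alone, so the tract-score comparison is biased in a direction the plan leaves open

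*Combined protocol and SAP*

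**What the plan says.** **Selection.** Section 1.3: "This study will target communities with high rates of respiratory infection or insufficient testing". Section 3.1 says the database identifies "neighborhoods that are at high risk for viral transmission because they are a hot spot or testing desert". Section 6.1 repeats that the community of interest is set by the hot-spot or testing-desert criteria together with weighted SVI.

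**Outcome.** Section 2.1, objective 1: "The hot-spot frequency and hot spot score trend will be measured for each census tract", in order to "determine if the screen and treat intervention has an impact on reducing hot spot identification or hot spot score". Objective 1a follows the score after each deployment in the visited tract and in an "SVI-matched census tract not receiving an intervention for 14-days following the screen and treat intervention". Section 6.3, although headed as secondary, names the hot-spot and desert scores as the efficacy variables.

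**Comparator.** Section 1.3: "Matched communities based on the census track-based SVI will be compared to assess impact of the screen and treat program on influenza rates". Section 6.5 likewise pairs on SVI and takes controls from tracts that receive no intervention during the study. Section 3.1 says the algorithm can "incorporate the social vulnerability index as an additional weighted measure to the hot spot or desert score", so SVI is one component of the score and viral activity is another.

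**Not specified.** No section randomises tracts, matches on or adjusts for the pre-deployment score, requires the control to be a hot spot at the same date, or names a model or test. Section 6.5 is the whole method of analysis.

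**The concern.** For a hot-spot deployment, the variable that selects the tract is also the variable that judges it. A visited tract starts flagged and high. A control with the same SVI usually does not, because matching on SVI leaves the viral-activity part of the score free to differ. High scores tend to drift back towards the average unaided, but within 14 days they usually do not return fully.

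The visited and control tracts would therefore differ even if the programme did nothing. Objective 1 asks about impact, so the answer for hot-spot deployments could not be attributed to the programme. Because the plan does not say whether level or change is compared, a choice made after the scores are seen would also choose the sign.

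**Working it through.** The plan gives no alpha, power, effect size, SD or number of tract pairs for this comparison, so there is no stated figure to reproduce. The check is a derivation followed by a simulation with zero effect.

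**1. Inputs from the documents.** About 140 tracked tracts and 20 partner community centres (Section 6.1). At least 2 deployments a week for about 12 weeks gives 2 × 12 = 24; the table in Section 6.1 lists 12.

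**2. Assumptions not in the documents.** The 14-day score correlation r (0.3 to 0.9), the hot-spot cut-off, how a tract is chosen among those that qualify, the weight of SVI in the score, normally distributed scores, and the 20 centres treated as 20 tracts. All visits below are hot-spot visits.

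**3. Derivation.** Standardise the score. Let g be the mean baseline gap, visited minus control. With no effect, the expected later gap is r × g. So:
- post-visit level bias ≈ r × g
- bias in change from baseline ≈ r × g − g = −(1 − r) × g

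Level bias minus change bias is always g. Unless g is zero, both cannot be zero.

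**4. Simulation.** The visited tract is a random choice among qualifying site tracts, the control is matched on SVI, and SVI is left out of the score. Units are SD.

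Top-20% cut-off:

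| r | Change bias | Level bias | Level − change (= gap) | Visited tracts still hot at 14 days |
|---|---|---|---|---|
| 0.3 | −0.94 | +0.48 | 1.42 | 32% |
| 0.5 | −0.68 | +0.75 | 1.43 | 42% |
| 0.7 | −0.41 | +1.04 | 1.45 | 52% |
| 0.9 | −0.14 | +1.38 | 1.52 | 71% |

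Top-40% cut-off:

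| r | Change bias | Level bias | Level − change (= gap) | Visited tracts still hot at 14 days |
|---|---|---|---|---|
| 0.3 | −0.64 | +0.34 | 0.98 | 52% |
| 0.5 | −0.46 | +0.58 | 1.04 | 59% |
| 0.7 | −0.28 | +0.78 | 1.06 | 68% |
| 0.9 | −0.10 | +1.02 | 1.12 | 81% |

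The rule in step 3 is approximate. For example, g = 1.43 and r = 0.5 give 0.5 × 1.43 = 0.715 in each direction, against −0.68 and +0.75 simulated.

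**5. Hot-spot frequency.** SVI controls stay level at 13–18% hot (top-20%) and 32–38% (top-40%). With the top-20% cut-off, the before-to-after fall in visited tracts is 100 − 71 = 29 to 100 − 32 = 68 points: a false fall. The post-visit comparison is 32–71% against 13–18%: false harm.

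**6. Sensitivity.** Separate runs with SVI in or out of the score gave change −0.98 to −0.12 and level +0.40 to +1.39 (top-20%), and change −0.67 to −0.08 and level +0.27 to +0.97 (top-40%). These agree with step 4 to within 0.1 SD. A further model always visited the two highest-scoring tracts, from a pool of 20 or 140, with SVI in the score. It gave larger biases: change −1.59 to −0.17 and level +0.56 to +2.08 over the same r. Adjusting that model for the baseline viral score and SVI, with the true correlation known, brought the bias to between −0.02 and +0.04 SD.

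**The case against.** **The plan may use pre-visit scores.** Objective 1 promises a score trend, and Section 3.1 describes a longitudinal database. A reader might infer that pre-deployment scores are left out of the analysis altogether; the text does not say that. What stands is narrower: no section specifies matching on them or adjusting for them. A trend that merely subtracts the pre-visit value is the form that regresses to the mean.

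**The direction is not fixed.** A reader might infer that the programme is bound to look falsely effective, or that hot-spot frequency is bound to show a false fall. Neither follows. Objective 1a, read literally, is a post-visit level and is biased against the programme. Post-visit frequency behaves the same way; only a before-to-after change in status shows a false fall.

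**The size is unknown.** This stands. At r = 0.9 the change bias is small, though the level bias is then largest. Desert visits in the mix would dilute a pooled result: if half the visits were desert visits unrelated to the score, the false fall would be 0.42 to 0.07 SD (top-20%) or 0.30 to 0.05 SD (top-40%). The simulation also equates centres with tracts, whereas Section 3.1 says only that the unit goes near the identified neighbourhood.

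**The study is called observational.** Sections 4.2 and 6.2 say so, but Sections 1.3 and 2.1 still set out to assess impact against controls, so the label does not remove the problem.

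**Conclusion.** The concern holds for the tract-score comparison in hot-spot deployments (objectives 1 and 1a). Selection on the score, an outcome on the score and matching on SVI alone give a biased comparison with no true effect, and the sign depends on an analysis the plan does not state. That conclusion needs only a baseline gap; for the change and level forms both to be unbiased, the gap would have to be zero.

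The size cannot be determined from the documents, because r, the cut-off, the tract choice, the SVI weight and the share of desert visits are not given. The simulated ranges are illustrations, not estimates of what this study will show.

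A reader might extend the point to the whole primary objective. The documents do not support that. The access aim and the household follow-up call (1b) do not rest on this comparison. Testing-desert tracts are chosen for low testing, so the mechanism does not carry over to them in the same form, although nothing in the plan shows that comparison to be unbiased either.

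**What to change.** Amend Sections 1.3, 2.1 and 6.5 before scores are analysed. For hot-spot deployments:

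1. Define the comparison as the score and hot-spot status in the 14 days after each deployment, adjusted for pre-deployment score, SVI and calendar week, with small-sample errors clustered by tract (for example a delete-one-tract jackknife).
2. At each deployment date, match the control on current score and hot-spot status as well as SVI.
3. Reconcile the control rules. Objective 1a can be read as barring intervention in the control for the following 14 days; Section 6.5 bars it for the whole study. State which applies. Allowing visits in the window would depart from that reading of 1a, so if it is allowed, say so and report how many controls are visited.
4. Report testing-desert deployments separately and without score matching, because Section 1.3 describes deserts as places where testing is too sparse to establish viral activity.
5. Report an estimate with its interval.

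**Cost.** Wording and some programming; the score is already tracked for about 140 tracts, and no patient procedure changes.

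**Downsides, from the simulations:**
- The SVI match loosens, to a mean gap of 0.03–0.08 instead of about 0.005 on the 0–1 scale.
- Residual bias is small, −0.07 to +0.04 SD.
- Item 3 is a trade-off. With 20 sites, never-visited controls give −0.01 to +0.08 SD of bias. Drawing controls instead from tracts not visited in the previous 14 days leaves 3–10% of them visited in their window, and a true 0.5 SD fall is then estimated as 0.42–0.48 SD. Both costs grow if any tract with SVI of at least 0.55 can be visited: bias of +0.02 to +0.30 SD under the first rule, and an estimate of 0.30–0.47 SD under the second.
- Precision is low. The SD of the estimate is 0.12–0.35 with 24 visits and 0.21–0.46 with 12, and with 24 visits a true 0.5 SD fall is significant in only 9% to 82% of runs.
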